7.6. Collection of Pregnancy Information

7.6.1. Time Period for Collecting of Pregnancy Information

Collection of Pregnancy Information:

 Pregnancy information will be collected on all pregnancies reported following administration of any washout product. Information on pregnancy identified during the screening phase and prior to washout product administration does not need to be collected.

7.6.2. Action to be Taken if Pregnancy Occurs

Action to be Taken:

- 1. The investigator will collect pregnancy information on any subject who becomes pregnant while participating in the study after administration of the washout product. The investigator will record pregnancy information on the appropriate form and submit it to GSKCH within 2 weeks of learning of the subject becoming pregnant. The subject will be followed to determine the outcome of the pregnancy. Information on the status of the mother and infant / neonate (including concomitant medications taken by the mother during the pregnancy) will be forwarded to GSKCH. Generally, follow-up will be no longer than 6 to 8 weeks following the estimated delivery date. Any termination of the pregnancy will be reported.
- 2. While pregnancy itself is not considered to be an AE, any pregnancy complication or elective termination for medical reasons will be recorded as an AE or SAE.
- 3. A spontaneous abortion is always considered to be an SAE and will be reported as such. An SAE occurring in association with a pregnancy, brought to the investigator's attention after the subject completed the study and considered by the investigator as possibly related to the investigational product, must be promptly forwarded to GSK.
- 4. While the investigator is not obliged to actively seek this information in former study participants, he or she may learn of an SAE through spontaneous reporting.
- 5. There is no requirement for the subject to be withdrawn from the study as a result of the pregnancy. However if they are withdrawn, this should be recorded in the appropriate section of the CRF.

Document Name	Rainbow Clinical Protocol.doc		
Туре	Version	Document Identifier	Effective Date
eldo controlled	4.0; Most-Recent; Effective; CURRENT	090032d580d464b0	23-May-2017 08:33:00
Reason For Issue	Auto Issue		

8. DATA MANAGEMENT

For this study subject data will be entered into an electronic case report form, using a GSKCH validated data system.

8.1. Source Documents/ Data

The source documents (e.g. clinical and office charts, laboratory notes, memoranda, subjects' diaries or evaluation checklists, dispensing records, recorded data from automated instruments, microfiches, photographic negatives, microfilm or magnetic media, subject files and records kept at the laboratory departments involved in the clinical study) which contain the source of data recorded in the eCRF should be specified in the Source Document Designation Form. In some cases the eCRF can be used as a source document.

Each subject will be assigned and identified by a unique Screening Number. Any reference made to an individual subject within the study must be done using the unique Screening Number.

8.2. Electronic Case Report Form

An eCRF is an electronic document designed to record all of the protocol required information to be reported to the sponsor on each trial subject.

For each subject who has given informed consent/assent and has been screened, an eCRF must be completed and signed by the Principal Investigator (or authorized designee) to certify that the data are complete and correct.

Management of clinical data will be performed in accordance with applicable GSKCH standards and data cleaning procedures to ensure the integrity of the data e.g. removing errors and inconsistencies in the data.

In order to protect the privacy of subjects, no Personally Identifiable Information (including the subject's name or initials or birth date) is to be recorded in the CRF or as part of the query text.

Adverse events and concomitant medications terms (if applicable) will be coded using MedDRA (Medical Dictionary for Regulatory Activities) and an internal validated medication dictionary, GSKDrug.

Subject data will be entered into GSKCH defined eCRFs and transmitted electronically to GSKCH in a validated (21 CFR Part 11 compliant) web-based electronic data capture system (InFormTM).

Document Name	Rainbow Clinical Protocol.doc		
Туре	Version	Document Identifier	Effective Date
eldo controlled	4.0; Most-Recent; Effective; CURRENT	090032d580d464b0	23-May-2017 08:33:00
Reason For Issue	Auto Issue		

All eCRF pages should be completed during a subject assessment when the eCRF has been designated as the source. Data that is sourced elsewhere should be entered into the eCRF in an agreed upon timeframe between the Investigator and Sponsor.

The eCRFs (including queries, query responses and audit trails) will be retained by GSKCH. Site data archived CDs prepared by a third party will be sent to the investigator to maintain as the investigator copy following the decommissioning of the study.

8.3. Data Handling

Documentation of all data management activities should allow step-by-step retrospective assessment of data quality and study performance. Any changes or corrections to data will be performed in the Electronic Data Capture (EDC) System, and it will include rationale for changes. The EDC system has an audit trail, which will provide a complete record of the changes and corrections endorsed by the Investigator.

8.3.1. Data Queries

Programmed edit checks will be generated automatically, as the data is being entered into the system. Data Management will also run reports and listings on the eCRF data, in addition to the queries already programmed and generated by the system, to raise manual queries as needed for site clarification or correction. The Clinical Dictionary Development and Management Group will raise queries as needed on safety data to code the terms (Adverse Events and Drugs) are reported appropriately.

The study monitor at the study site will review the eCRFs in accordance with the monitoring plan, and any queries will be generated in the EDC System to the Investigator or designee, enabling the errors to be addressed in parallel with Data Management review. Monitor can also run reports and listings on the eCRFs, to raise manual queries as needed for site clarification or correction.

Document Name	Rainbow Clinical Protocol.doc		
Туре	Version	Document Identifier	Effective Date
eldo controlled	4.0; Most-Recent; Effective; CURRENT	090032d580d464b0	23-May-2017 08:33:00
Reason For Issue	Auto Issue		

9. STATISTICAL CONSIDERATIONS AND DATA ANALYSES

9.1 Sample Size Determination

Approximately 200 female subjects aged 18-45 with self-assessed sensitive skin and a minimum of $10 \ 8$ and a maximum of 25 facial blemishes (papules and pustules, excluding the nose) will be screened to randomise 132 healthy subjects, to ensure approximately 40 subjects in the test product regimen, 40 subjects in the no treatment regimen and 40 subjects in the positive control regimen complete the study (Assuming a 10% dropout rate). Randomisation will be stratified by age (<21 years old, ≥ 21 years of age).

The sample size was based on clinical considerations. In a previous study of a cosmetic product, counts of papules and pustules decreased from a baseline mean of 27.6 to a mean of 13.5 at Week 8 (ref. Shalita 1995 IJD). With 40 subjects in both the test product and no-treatment regimens, a difference between groups at least 60% the magnitude of the standard deviation (assumed equal for both groups) would be detectable at two-sided alpha=0.05 with approximately 80% power.

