9.2. General Considerations

Statistical testing for the endpoints in this study will be conducted at unadjusted two-sided alpha=0.05. While for this proof of concept study statistical significance (p<0.05) may not be achieved, these results will drive sample size projections for future studies. Due to the exploratory nature of the study, no adjustment to the alpha level for multiple comparisons will be made. P-values resulting from inferential testing will be considered primarily as summary statistics.

No statistical comparisons between the positive control regimen and the test product regimen are planned. The positive control is included to provide internal validation to the trial and to provide a reference point for estimates of effect size.

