9.2.1. Definition of Analysis Populations

The 'Intent to treat' (ITT) population includes all subjects who are randomised into the study and have at least one post-baseline measurement available. All efficacy analyses will be based on the ITT population.

The Per Protocol (PP) population will consist of the subset of ITT subjects which excludes those subjects with significant protocol deviations. Protocol deviations will

Document Name	Rainbow Clinical Protocol.doc		
Туре	Version	Document Identifier	Effective Date
eldo controlled	4.0; Most-Recent; Effective; CURRENT	090032d580d464b0	23-May-2017 08:33:00
Reason For Issue	Auto Issue		

be identified prior to database unblinding and will include, but not be limited to, non-compliance with the protocol or product application and use of prohibited concomitant medications. Confirmatory analyses of at least the primary efficacy endpoint will be performed on the PP population.

The Safety population will include all subjects who applied any of the study products. All safety analyses will be performed using the Safety population. For the no treatment regimen, this will include any use of the cleanser post-randomisation.

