9.2.3. Criteria for Evaluation

The primary objective will be to assess the skin moisturisation potential of the test product formulation compared to no treatment based on change from baseline in corneometry 8 hours after the first application of test product. Given this proof of concept study, the study will be considered a success if at least a trend in favor of the test product is observed. Other efficacy evaluations will be similarly assessed for success.

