9.3.2. Primary Analysis(es)

The primary endpoint is the change from baseline in Corneometer measurement at 8 hours following the first product application (use of cleanser for the no treatment regimen). Data for the endpoint will be summarized by age stratum and treatment

Document Name	Rainbow Clinical Protocol.doc		
Туре	Version	Document Identifier	Effective Date
eldo controlled	4.0; Most-Recent; Effective; CURRENT	090032d580d464b0	23-May-2017 08:33:00
Reason For Issue	Auto Issue		

regimen using means and 95% confidence intervals and compared between treatment regimens using analysis of covariance (ANCOVA) with treatment main effect, age stratum (<21, ≥21 years of age) and baseline measurement as covariate or Wilcoxon rank sum test, depending on the data distribution. Differences between least squares means for the test product and no treatment regimen will be presented, together with 95% confidence intervals.

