4.5 Analysis of Secondary Objectives

4.5.1 Efficacy

The change from baseline in corneometer measurements at 1 and 3 hours following the first product application as well as at Weeks 1, 4 and 8 will be analysed at each post-baseline time point using the same ANCOVA model as in primary analysis. Differences between least squares means for (i) test product and no treatment regimen; (ii) positive control and no treatment regimen will be presented, together with 95% confidence intervals. The normality assumption for ANCOVA will be checked. If violated, non-parametric method such as Wilcoxon rank sum test may be applied.

The sebumeter and sebumeter excretion rate changes from baseline at Weeks 1, 4 and 8 will be analysed at each post-baseline visit using ANCOVA with treatment main effect, age stratum (<21, ≥21 years of age) and baseline count as covariate. Differences between least squares means for (i) test product and no treatment regimen; (ii) positive control and no treatment regimen will be presented, together with 95% confidence intervals (Table 14.2.3.1 for sebumeter, Table 14.2.4.1 for sebumeter excretion rate). The normality assumption for ANCOVA will be checked. If violated, non-parametric method such as Wilcoxon rank sum test may be applied.

Clinical assessment of blemish counts (papules and pustules) change from baseline at Weeks 1, 4 and 8 will be analysed at each post-baseline visit using ANCOVA with treatment main effect, age stratum (<21, ≥21 years of age) and baseline count as covariate. Differences between least squares means for (i) test product and no treatment regimen; (ii) positive control and no treatment regimen will be presented, together with 95% confidence intervals (Table 14.2.5.1 for the ITT population and Table 14.2.5.4 for the PP population). The normality assumption for ANCOVA will be checked. If violated, non-parametric method such as Wilcoxon rank sum test may be applied. A figure will be provided for blemish profile of the ITT population (Figure 14.2.1).

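### The stated 80% power does not follow from 40 completers per arm and 0.60 SD, which give 75.5 to 76.5%; 80% at that size corresponds to about 0.63 SD

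*Protocol*

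**What the plan says.** Protocol 9.1 plans to randomise 132 subjects and assumes 10% dropout, so that about 40 per regimen finish, among them "40 subjects in the no treatment regimen and 40 subjects in the positive control regimen complete the study". The power sentence then reads "With 40 subjects in both the test product and no-treatment regimens, a difference between groups at least 60% the magnitude of the standard deviation" (the SD being taken as equal in both groups) "would be detectable at two-sided alpha=0.05 with approximately 80% power". The sentence names no test, gives no numerical SD, and mentions neither covariate adjustment nor a baseline correlation. It is repeated in the protocol synopsis, protocol 3.3 and SAP 1.4.

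Other sections bear on how much this matters:

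- Protocol 9.3.2: "The primary endpoint is the change from baseline in Corneometer measurement at 8 hours following the first product application".
- Protocol 9.2.1: the ITT population "includes all subjects who are randomised into the study and have at least one post-baseline measurement available".
- Protocol 9.2: "P-values resulting from inferential testing will be considered primarily as summary statistics".
- Protocol 9.2.3: "the study will be considered a success if at least a trend in favor of the test product is observed".
- The primary analysis is ANCOVA with baseline and age stratum. SAP 4.5.1 says that the secondary corneometer changes "will be analysed at each post-baseline time point using the same ANCOVA model as in primary analysis".

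**The concern.** The sentence supplies a sample size, a standardised difference, an alpha and a power. Any three of these fix the fourth, so the statement can be checked on its own terms. Forty per arm is rather few for 80% power at 0.60 SD. The 40 is also explicitly the number left after dropout, which raises the possibility that the power was worked out for the number randomised and then attached to the number of completers.

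What is at stake is an accurate link between sample size, detectable difference and power. Protocol 9.2 says that the results will drive sample size projections for future studies, so a reader may well reuse this one.

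**Working it through.** **Inputs (Protocol 9.1; same in SAP 1.4).** n = 40 per arm, d = 0.60 SD, common SD, two-sided alpha 0.05, stated power about 80%. Randomised: 132, which is 132/3 = 44 per arm if allocation is equal (an assumption, since the ratio is not stated). Completers: 132 × 0.9/3 = 39.6 per arm, in line with the stated 40.

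**1. Power from the stated inputs.** The noncentrality is d√(n/2) = 0.60 × √20 = 2.683.

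- Normal approximation: Φ(2.683 − 1.960) = Φ(0.723) = **76.5%**.
- Two-sample t test, df = 78, noncentral t: **75.5%**.
- Simulation of 100,000 two-sample t tests: 75.7%.

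The stated figure is not reproduced. The shortfall is 3.5 points (normal) to 4.5 points (t).

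**2. Detectable difference at 80% power, 40 per arm.**

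- Normal: (1.960 + 0.842) × √(2/40) = **0.626 SD**.
- t: **0.634 SD**.

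**3. Sample size for 80% power at 0.60 SD.**

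- Normal: 2 × (1.960 + 0.842)²/0.60² = **43.6** per arm.
- t: **44.6** per arm.

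**4. Power at 0.60 SD by number per arm.**

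| Per arm | t | Normal |
|---|---|---|
| 40 (completers) | 75.5% | 76.5% |
| 43 | 78.5% | 79.4% |
| 44 (randomised) | 79.5% | 80.4% |
| 45 | 80.4% | 81.2% |

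The stated 80% matches 44 per arm. That it was calculated on the randomised number is an inference; the documents do not say so.

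**5. Other readings at 40 per arm and 0.60 SD.**

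| Variant | Power |
|---|---|
| Error df pooled over three arms (117) | 75.8% |
| Wilcoxon, relative efficiency 0.955 | 73.5 to 74.6% |
| One-sided alpha 0.05 | 84.5 to 85.0% (contradicts the stated two-sided test) |

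None of these gives 80%. Readings that use baseline adjustment need a correlation that the plan does not give; they are taken up with the objection.

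**The case against.** The strongest reply is that the trial does not plan an unadjusted comparison. The planned model is ANCOVA with baseline as covariate, and the sentence does not say which SD it means. Let ρ be the correlation between baseline and follow-up, with equal variances at both times and 115 error df. Power at 40 per arm is then:

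| Meaning of SD | Difference in residual SDs | Power |
|---|---|---|
| Change-score SD | 0.60 × √(2/(1+ρ)) | 96% at ρ = 0; 87% at 0.5; 82% at 0.7; 80% at 0.8; 78% at 0.9 |
| Raw follow-up SD | 0.60/√(1−ρ²) | 80% at ρ = 0.3; 87% at 0.5 |
| Residual SD | 0.60 | 75.8% |

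The planned analysis may therefore reach 80% or more, and nothing here shows that the trial is underpowered. That part stands. It does not rescue the sentence, because the plan states neither ρ nor the SD, and the possible values run from about 76% to 96%.

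A second reply is that the text says approximately, and 0.60 is close to 0.63. The gap in SD units is indeed small. A 3.5 to 4.5 point shortfall in power is still more than that word comfortably covers, and 0.63 would have been as easy to write.

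Third, the primary endpoint falls on Day 1, before 8-week dropout has much effect, so about 44 per arm should contribute and power is close to 80% even without adjustment. This stands and limits the weight of the point. It also confirms that the number matching 80% is 44, where the sentence names 40.

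Fourth, no decision turns on it: the study is exploratory, a trend counts as success, and the size was set on clinical considerations. This too stands, and is why the point is minor.

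**Conclusion.** The power statement is wrong as written. Its own inputs give 75.5 to 76.5%, so type II error is about 24%. The difference detectable with 80% power is about 0.63 SD (0.626 to 0.634).

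This rests on reading the sentence as an unadjusted two-group comparison of a continuous endpoint with equal SDs, the only reading that needs no input beyond those given. It checks a stated figure against its stated inputs. It is not an estimate of the power of the planned ANCOVA, nor of the repeated-measures logistic regression for the lay-person assessment, which is binary. The severity is minor: a figure to correct, with no flaw in the design.

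**What to change.** In the protocol synopsis, protocol 3.3, protocol 9.1 and SAP 1.4, replace the power sentence with wording such as:

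> Forty completers per arm give 80% power for a difference of about 0.63 SD (about 75 to 77% for 0.60 SD), for an unadjusted two-group comparison of a continuous endpoint at two-sided alpha 0.05.

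Optionally add that the roughly 44 randomised per arm expected to contribute to the Day 1 8-hour primary endpoint give about 80% at 0.60 SD, assuming equal allocation. Neither figure should be attached to the Week 8 endpoints as a class, since these include a binary outcome.

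Naming the comparison matters because the planned model is ANCOVA. If the sponsor would rather state power for ANCOVA, the text must say which SD is meant and what baseline correlation is assumed.

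The cost is wording in four places and a slightly less favourable figure. No extra subjects and no change of design or analysis are needed. Since the SAP addendum post-dates unblinding, the main use of the correction now is in the study report and in planning later studies.

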9.2. General Considerations

Statistical testing for the endpoints in this study will be conducted at unadjusted two-sided alpha=0.05. While for this proof of concept study statistical significance (p<0.05) may not be achieved, these results will drive sample size projections for future studies. Due to the exploratory nature of the study, no adjustment to the alpha level for multiple comparisons will be made. P-values resulting from inferential testing will be considered primarily as summary statistics.

No statistical comparisons between the positive control regimen and the test product regimen are planned. The positive control is included to provide internal validation to the trial and to provide a reference point for estimates of effect size.

9.2.1. Definition of Analysis Populations

The 'Intent to treat' (ITT) population includes all subjects who are randomised into the study and have at least one post-baseline measurement available. All efficacy analyses will be based on the ITT population.

The Per Protocol (PP) population will consist of the subset of ITT subjects which excludes those subjects with significant protocol deviations. Protocol deviations will

Document Name	Rainbow Clinical Protocol.doc		
Туре	Version	Document Identifier	Effective Date
eldo controlled	4.0; Most-Recent; Effective; CURRENT	090032d580d464b0	23-May-2017 08:33:00
Reason For Issue	Auto Issue		

be identified prior to database unblinding and will include, but not be limited to, non-compliance with the protocol or product application and use of prohibited concomitant medications. Confirmatory analyses of at least the primary efficacy endpoint will be performed on the PP population.

The Safety population will include all subjects who applied any of the study products. All safety analyses will be performed using the Safety population. For the no treatment regimen, this will include any use of the cleanser post-randomisation.

9.2.2. Exclusion of Data from Analysis

No data will be excluded from any analysis.

9.2.3. Criteria for Evaluation

The primary objective will be to assess the skin moisturisation potential of the test product formulation compared to no treatment based on change from baseline in corneometry 8 hours after the first application of test product. Given this proof of concept study, the study will be considered a success if at least a trend in favor of the test product is observed. Other efficacy evaluations will be similarly assessed for success.

9.2.4. Handling of Dropouts and Missing Data

Missing data will not be replaced or imputed. Dropouts will be included in analyses up to the point of discontinuation.

9.3. Statistical Methods and Analytical Plan

Additional details of the proposed statistical analysis will be documented in the statistical analysis plan (SAP), which will be written following finalization of the protocol and prior to study unblinding / analysis (as appropriate).

9.3.1. Demographic and Baseline Characteristics

Age and baseline characteristics (corneometry, blemish counts, sebumetry) will be summarised descriptively by treatment regimen (test product, positive control, no treatment) using means, medians and standard deviations. Race and Fitzpatrick Skin Type will be summarised by treatment regimen using frequency counts and percentages.

